### Preparation for surgery:

- 1. Prior to surgery, review inclusion/exclusion criteria and ensure subject has been properly consented for participation in the study. Refer to Sections 10.1 and 10.2. Also, document any changes to ocular and non-ocular concomitant medications.
- 2. Perform slit lamp examination prior to surgery.
- 3. Prepare subject/eyes for surgery in accordance with site specific operating procedures.
- 4. Ensure the investigational device to which the subject is randomized is utilized for the surgery.

### **Procedures related to laser surgeries:**

Laser systems and surgeries should be performed according to the Operator's (or User's) and Procedure's manuals. Refer to the manuals for specific instructions for device set up and

Effective Date: 19-Mar-2017 Page 57 of 81 Alcon - Business Use Only Protocol - Clinical

Version: 2.0; Most-Recent; Effective; CURRENT Document: TDOC-0052425

Status: Effective

maintenance to ensure proper function prior to treatment.

1. Ensure the Laser System is calibrated per manufacturer's instructions prior to the procedure.

- 2. Ensure that treatment parameters are precisely transferred from the files to the laser system.
  - *NOTE:* Treatment target is emmetropia for all eyes.
- 3. Perform surgery under topical anesthesia as per the normal routine of the surgeon.
  - *NOTE*: Although the surgery is planned to be bilateral, in the case where the Investigator decides to not perform the surgery on the second eye on the same day the first eye is treated, the Investigator may treat the second eye at a later date while the subject is still in the study. In this case, effectiveness and safety assessments will be conducted as per post-surgery follow up visits if the fellow eye is treated with the study treatment. If the fellow eye is not treated at all or treated with a non-study treatment, AEs will only be collected for this eye. Refer to the MOP Table 4-1 for further details.
- 4. Record any AEs and device deficiencies. Refer to Section 13 for further details. *NOTE:* SAEs must be entered into EDC within 24 hours of the Investigator's knowledge. OTHER NOTES:
- Record the method of flap creation for the Topography guided LASIK surgery (microkeratome blade or femtosecond laser) in source document.
- Record operating room temperature and environmental conditions control in source document.
- Record all surgical medications used during the procedure in source document.
- Record surgical problems or complications that occur during surgery in source document.
- Record any other procedures during surgery in source document.
- Record the surgeon who performed the surgery. No more than two surgeons per site should perform a type of surgery.

### 12.1.3 Post-Surgery follow-up Visits (Day 1, Week 1, Months 1, 3 and 12)

Below is a list of study procedures to be undertaken at the Post-Surgery follow-up Visits (Day 1, Week 1 [Day 5 to Day 9], Months 1 [Day 21 to Day 35], 3 [Day 70 to Day 98] and 12

Effective Date: 19-Mar-2017 Page 58 of 81 Alcon - Business Use Only Protocol - Clinical

Version: 2.0; Most-Recent; Effective; CURRENT Document: TDOC-0052425

Status: Effective

[Day 330 to Day 375]). Procedures must be performed in the order presented below unless otherwise stated. All ocular assessments must be done monocularly.

- 1. Record any changes to subjects' ocular and non-ocular medical history or concomitant medications at all visits.
- 2. Administer the RSVP Questionnaire at the Month 1, 3, and 12 visits.
- 3. Administer the SQDES Questionnaire at the Month 1, 3, and 12 visits.

NOTE: Investigators and site staff must review both questionnaires results prior to subjects leaving the office to ensure completeness.

- 4. Conduct the following procedures in an order that is feasible for your site:
  - Perform lighting measurements for VA and contrast sensitivity testing at all visits.
  - Measure distance UCVA in photopic conditions at all visits.
  - Measure uncorrected contrast sensitivity in mesopic conditions at the Month 1, 3, and 12 visits.
  - Measure manifest refraction at 4 meters and adjust for optical infinity at the Week 1, Month 1, 3, and 12 visits.
  - Measure distance BCVA in photopic conditions at the Week 1, Month 1, 3, and 12 visits.
- 5. Conduct the following procedures in an order that is feasible for your site:
  - Perform topography at the Month 1, 3, and 12 visits.

- 6. Perform slit lamp examination at all visits.
- 7. Measure IOP at the Month 1, 3, and 12 visits.
- 8. Perform dilated fundus examination at Month 12.
- 9. Record any AEs at all visits. Refer to Section 13 for further details.

*NOTE*: SAEs must be entered into EDC within 24 hours of the Investigator's knowledge.

*NOTE:* Secondary Surgical Intervention: Retreatments will not be allowed in this study.

Effective Date: 19-Mar-2017 Page 59 of 81 Alcon - Business Use Only Protocol - Clinical

Version: 2.0; Most-Recent; Effective; CURRENT Document: TDOC-0052425

Status: Effective

#### **Unscheduled Visits** 12.2

If a subject is examined more than once during any of the scheduled follow-up periods, or between scheduled follow-up periods, an unscheduled visit (UNSV) form should be completed reporting any study parameters or any relevant data collected at this visit.

An UNSV is defined as one that meets all of the following:

- Examination that is not standard of care and not required by the protocol
- Examination conducted by the study staff
- New finding, continuation of an existing finding, or a change to a previous finding is noted

An UNSV may or may not result in the capture of an AE. Likewise, an AE may be captured without the report of an UNSV (e.g. AE identified subsequent to study eye examination by non-study personnel).

The assessments captured at the UNSV are dictated by the Investigator per his/her medical judgment. The following assessments/documentation are recommended.

- Changes to subjects' ocular and non-ocular medical history or concomitant medications
- Slit lamp examination
- Manifest refraction
- Distance UCVA
- Fundus examination
- IOP
- AEs

*NOTE*: Assessments/ documentation are not limited to the above list.

If the subject is discontinued at the UNSV, then all early exit procedures must be performed (refer to Table 6–1).

For safety purposes, if an UNSV is required after the final study visit (Month 12), then the visit will be documented in the source documents.

Effective Date: 19-Mar-2017 Page 60 of 81 Alcon - Business Use Only Protocol - Clinical

Version: 2.0; Most-Recent; Effective; CURRENT Document: TDOC-0052425

Status: Effective

#### 12.3 Missed Visits

If a subject misses a scheduled visit, the subject should be rescheduled within allowed window for the same visit. Diligence should be shown in trying to schedule the subject for all visits, and all attempts to contact the subject documented in the subject's chart. In documentation, include dates, times, method of contact, etc. If attempts to contact the subject are unsuccessful, the date the subject is considered lost to follow-up must be documented. If a subject is unable to return for the final study visit, the Exit eCRF with the appropriate reason for discontinuation indicating the subject is lost to follow-up will be completed.

#### 12.4 **Discontinued Subjects**

Discontinued subjects are those who withdraw, or are withdrawn from the study after signing the ICF and prior to completing all study visits. Subjects signing consent, but withdraw or are withdrawn prior to randomization will be considered discontinued due to screen failure, and the failed entry criterion must documented in source document and EDC (refer to Section 10).

Subjects may discontinue study participation at any time and for any reason. Subjects who complete the laser treatment in either eye will not be discontinued by the Investigator.

Subject numbers from discontinued subjects will not be reissued. Discontinued subjects will not be replaced.

It is the Investigator's responsibility to select only those subjects who are likely to be both willing and able to complete the required follow-up for participation in this study.

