### 9.2.1 **Procedures Per Study Visit**

The clinical study procedures to be conducted at each study visit are listed in Table 6–1 and detailed in Section 12. Further details on the actual assessments are provided in full in the Manual of Procedures (MOP) for this study. A brief summary of the procedures performed by visit is provided here.

*NOTE*: All assessments performed at the eye level as listed in Table 6–1 will be done monocularly.

At the Pre-Surgery Visit (Day -45 to Day -1) the subject will sign the informed consent form (ICF). Standard procedures will be performed to determine subject eligibility. The subject will be evaluated against all entry criteria. The subject status (e.g., continuing or screen failure) will be documented and the subject's data will be entered into electronic data capture (EDC) at the time of consent to assign subject number. For continuing subjects:

- 1. The subject will be randomized to Topography Guided LASIK or SMILE in the EDC system.
- 2. The subject will be provided with pre-surgery information and medications in accordance with investigational site's standard of care.
- 3. The Investigator will consider any unresolved complications or events in either eye prior to surgery.
- 4. The Surgery Visit (Day 0) will be scheduled to occur within 45 calendar days of the Pre-Surgery Visit (Screening).

Print Date: Printed By:

Effective Date: 19-Mar-2017 Page 43 of 81 Alcon - Business Use Only Protocol - Clinical

Version: 2.0; Most-Recent; Effective; CURRENT Document: TDOC-0052425

Status: Effective

a. Inclusion/ exclusion criteria will be reviewed prior to surgery to ensure subjects are still eligible for the study (see Section 10.1 and 10.2). Subjects failing to pass entry criteria will not be re-screened. If a subject is excluded post-randomization and prior to the laser touching the eye (defined as once flap creation is initiated for LASIK and once laser touches the eye for SMILE), the subject should be discontinued from participation in the study.

- b. The surgery will be performed on both eyes. The subject will be prepared for surgery in accordance with site specific operating procedures.
- 5. After surgery, the ocular and/or non-ocular concomitant medication will be administered as per Investigator's standard procedures.

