#### 9.3 Risk Benefit Assessment

#### 9.3.1 **Potential Risks**

### LASIK and SMILE

The risks of LASIK are well known, however, the risks of SMILE are still being investigated because it is a newer procedure (Sekundo 2011, Solomon 2009).

Some risks are similar for LASIK and SMILE. First, the laser could malfunction and the procedure would need to be stopped before completion. If this happens, a second surgical procedure may be needed. Second, LASIK and SMILE may not fully correct, or may overcorrect the refractive error, leaving the subject with some residual refractive error.

Alcon - Business Use Only Protocol - Clinical Effective Date: 19-Mar-2017
Page 44 of 81

Document: TDOC-0052425 Version: 2.0; Most-Recent; Effective; CURRENT

Status: Effective

Undercorrection or overcorrection may be treatable by performing a second refractive surgery. Additionally, decentration of the treatment as a result of off-center placement of the laser may occur, which could affect the outcome and consequently the subject's vision.

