### **SMILE**

Ivarsen et al (Ivarsen 2014) performed a study to evaluate the safety of SMILE. A total of 1574 eyes were treated with SMILE and followed for 3 months. In this study, the pre-surgery complications reported in at least one eye were as follows:

- Abrasion at the incision
- Lenticule extraction difficulties
- Minor tear at the incision
- Suction loss
- Central abrasion
- Cap perforation
- Major tear

Effective Date: 19-Mar-2017 Page 45 of 81 Alcon - Business Use Only Protocol - Clinical

Version: 2.0; Most-Recent; Effective; CURRENT Document: TDOC-0052425

Status: Effective

Impossible lenticule extraction

The post-surgery complications reported in at least one eye were as follows:

- Haze
- Dry surface
- Epithelial islands at incision
- Fiber in the interface
- Infiltrates/keratitis
- Monocular ghost images
- Interface inflammation

In general, these complications may be minimized by sufficient proficiency in performing the SMILE procedure, and laser setting optimization.

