## 11 TREATMENT

The treatment in this study involves the use of either the EX500 for Topography Guided LASIK or the VisuMax for SMILE as described in Table 11–1.

For the purposes of this study, treatment will be considered to have begun once the flap creation is initiated for LASIK and once the laser touches the eye for SMILE.

Alcon - Business Use Only Protocol - Clinical Effective Date: 19-Mar-2017 Page 49 of 81

Document: TDOC-0052425 Version: 2.0; Most-Recent; Effective; CURRENT

Status: Effective

Table 11–1 Treatments

	Test Article: Wavelight EX500 for Topography Guided LASIK	Control Article: Zeiss VisuMax for SMILE
Administration	The EX500 laser is used to ablate the corneal stroma which results in the refractive error correction. Prior to ablation, the corneal flap may be created with a femtosecond laser or microkeratome blade at the surgeon's discretion.  Treatment planning will be based on topography.	The VisuMax Laser keratome is used to create a lenticule in the corneal stroma and a channel for the removal of the lenticule. Removal of the lenticule results in the refractive error correction.
Duration of treatment	The treatment is intended to last the subject's lifetime.	The treatment is intended to last the subject's lifetime.

The Investigator will be responsible for ensuring that the EX500 and VisuMax Laser Systems are used in accordance with their indications and procedural guidance provided in their respective Operator's (or User's) and Procedure's Manuals by a licensed ophthalmologist with LASIK and/or SMILE surgery experience. A summary of the necessary training and experience needed to use the investigational device must be recorded at the site.

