# **15.2** Analysis Data Sets

The following analysis sets will be defined for this study: intention to treat (ITT) and safety analysis set. Assignment of study eyes to the appropriate analysis set(s) will be determined prior to DBL.

The ITT analysis set will contain all study eyes for which study treatment has begun for the set of subjects that are randomized. For the purposes of this study, the treatment will be considered to have begun once the flap creation is initiated for LASIK and once laser touches the eye for SMILE.

All eyes in the ITT analysis set will be assigned to the treatment to which they are randomized.

The safety analysis set will contain all study eyes for which study treatment has begun; all eyes in the safety analysis set will be assigned to the treatment actually received. In general, the ITT analysis set will be used to display subject disposition, demographics and baseline characteristics, medical history and the analysis of the effectiveness endpoints. The safety analysis set will be used for the analysis of the safety endpoints.

Alcon - Business Use Only Protocol - Clinical Effective Date: 19-Mar-2017 Page 70 of 81

Document: TDOC-0052425 Version: 2.0; Most-Recent; Effective; CURRENT

Status: Effective

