## 15.5 Handling of Missing Data

The primary analysis of the effectiveness endpoints will be based on observed data (i.e. no imputation will be performed). The influence of missing data is expected to be minimal.

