5.5 Handling of Missing Data

The analyses of the effectiveness endpoints will be based on observed data (i.e. no imputation will be performed). The influence of missing data is expected to be minimal.

6 Safety Analysis Strategy

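### Investigator withdrawal is barred only once laser treatment is complete in an eye, but ITT starts when treatment has begun, so some begun-but-incomplete eyes can leave the Month 3 primary denominator

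*Protocol*

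**What the plan says.** Protocol 12.4 protects subjects from investigator withdrawal in one circumstance: "Subjects who complete the laser treatment in either eye will not be discontinued by the Investigator". The same section counts as discontinued both those who withdraw and those who are withdrawn, so withdrawal by the investigator is a recognised route.

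Protocol 11 sets an earlier boundary: "treatment will be considered to have begun once the flap creation is initiated for LASIK and once the laser touches the eye for SMILE". The analysis sets use it. Protocol 15.2 reads "The ITT analysis set will contain all study eyes for which study treatment has begun for the set of subjects that are randomized", SAP 3 agrees for both the ITT and Safety sets, and SAP 6.3.1 starts the treatment-emergent AE period at the same point.

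Instructions to discontinue apply before treatment starts. Protocol 9.2.1 begins "If a subject is excluded post-randomization and prior to the laser touching the eye" and defines that moment for LASIK as flap initiation. The closing note of 12.1.1 and the opening of 12.1.2 speak of laser contact and do not repeat that definition.

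On missing data, Protocol 15.5 says "The primary analysis of the effectiveness endpoints will be based on observed data (i.e. no imputation will be performed"; SAP 5.5 says the same of all effectiveness analyses.

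Interrupted procedures are foreseen. Protocol 9.3.1 warns for both arms that "the laser could malfunction and the procedure would need to be stopped before completion", describes LASIK flap complications that may lead to a switch to PRK, and lists suction loss and "Impossible lenticule extraction" among complications in a cited SMILE series.

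**The concern.** A subject whose procedure is begun and then stopped, with neither eye completed, falls between two rules: inside ITT, outside the protection of 12.4. The person who may withdraw that subject knows the assignment, because Protocol 7.2 and SAP 1.4 mask only the staff who perform manifest refraction and UCVA testing. The protocol also gives a practical reason to exit: 9.3.1 says a stopped procedure may call for a second one, while 9.1, 9.2.1 and 12.1.3 bar re-treatment in the study.

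Inclusion criterion 4 requires at least 0.75 D of manifest cylinder in each eye, so an eye that received no correction would be expected to miss the 0.5 D threshold. Removing it before Month 3 raises that arm's observed success rate. The two procedures fail in different ways, so equal loss cannot be presumed. What is at stake is missingness that is related to outcome and decided by unmasked staff.

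**Working it through.** **Step 1. The boundaries side by side**

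| Place | Trigger | Consequence |
|---|---|---|
| Protocol 9.2.1 | before flap initiation (LASIK) or laser touch (SMILE) | subject should be discontinued |
| Protocol 12.1.1, closing note | complication before any laser contact | subject should be discontinued |
| Protocol 12.1.2 | excluded before surgery, explained as no laser contact | subject must be discontinued |
| Protocol 11 and 15.2, SAP 3 | flap initiated or laser touches the eye | eye is in ITT and Safety |
| Protocol 12.4 | laser treatment complete in either eye | investigator may not discontinue |

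Two gaps follow.

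- *Begun, completed in neither eye.* The subject is in ITT. No text requires withdrawal and none forbids it.
- *Blade flap.* Protocol 11.2 allows a microkeratome blade. A complication during such a flap comes after initiation (in ITT) but before laser contact (discontinue, under 12.1.1). Only 9.2.1 supplies the definition that would resolve this. This route exists only in the LASIK arm.

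**Step 2. Why the eye leaves the primary analysis**

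Table 6-1, footnote k, asks for Month 12 procedures at early exit, and SAP 2.4 lists unscheduled data. No visible text lets either stand in for Month 3 (Day 70 to 98). Under observed-data analysis the eye then has no primary outcome. Separately, Protocol 12.1.2 limits collection to AEs for a fellow eye given a non-study treatment; if that covers a fellow eye begun and then converted, it could be in ITT without a Month 3 refraction even with no withdrawal.

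**Step 3. The plan's own sample size**

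Inputs (Protocol 15.9, SAP 7): 90% vs 80%, ICC 0.39, two-sided 5%, 90% power, 7% post-surgery dropout.

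- Independent eyes per arm, pooled variance, no continuity correction: [1.960 × √(2 × 0.85 × 0.15) + 1.282 × √(0.09 + 0.16)]² / 0.10² = 266.
- Subjects per arm: 266 × 1.39 / 2 = 184.9, so 185. The plan's figure reproduces.
- Dropout: 185 / 0.93 = 199, against 200 planned; 200 × 0.93 = 186 expected at Month 3.
- Effective eyes per arm: 186 × 2 / 1.39 = 267.6, held fixed below.

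**Step 4. Overstatement of one arm's rate**

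The documents give no abort rate, so q is an assumed share of the arm's eyes that are begun, not completed and lost, all of which would fail. With p the rate among the remaining eyes, overstatement = p − p(1 − q) = p × q.

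| q | p = 80% | p = 90% |
|---|---|---|
| 0.5% | 0.4 points | 0.45 points |
| 1% | 0.8 | 0.9 |
| 2% | 1.6 | 1.8 |

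For scale, 2% of 400 eyes is 8 eyes. That is 4 subjects if both eyes were begun. With one begun eye each it is 8 subjects, or 4% of the 200 treated, against a dropout allowance of 7% × 200 = 14.

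**Step 5. Direction and effect on the test**

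With 90% and 80% among completed eyes, the observed difference is 10.0 points and planned power is 0.90. Counting the lost eyes as failures gives:

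- 1% in LASIK only: 9.1 points, power 0.83
- 2% in LASIK only: 8.2 points, power 0.74
- 2% in both arms: 9.8 points, power 0.86
- 2% in SMILE only: 11.6 points, power 0.96

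Now suppose both arms truly have 80% success among all begun eyes. The SAP's success criterion needs significance in favour of LASIK, nominally 0.025 under no difference. With d = 0.80/(1 − q) − 0.80 and a normal approximation, LASIK-only loss gives 0.042 (q = 1%), 0.069 (2%), 0.110 (3%) and 0.245 (5%). SMILE-only loss of 2% gives 0.007. Equal loss leaves 0.025.

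**The case against.** The strongest reply is that the first gap is permission by silence. No passage tells an investigator to withdraw a subject once treatment has begun by the protocol's definition, and the post-surgery schedule assumes follow-up. The affected group is narrow: a completed fellow eye protects the subject, and 12.1.2 lets the second eye be treated later. That stands, and the share lost may be zero.

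Several stronger readings are tempting, and the documents do not support them.

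- *That these eyes vanish from the trial.* They remain in ITT and Safety, the disposition table (SAP 4.1), AE reporting (SAP 6.3.1) and the surgical-problems summary (SAP 6.3.8). Exit assessments are called for. What is lost is the Month 3 value and later scheduled follow-up.
- *That the gap favours LASIK.* The SMILE events in 9.3.1, if they led to loss, would raise the SMILE rate and work against the claim. Nor does the protocol say those cases were abandoned; where extraction fails, the laser step may already be complete, since 11.2 has the laser create lenticule and incision in one step.
- *That every such eye would fail.* An eye converted to another procedure may reach 0.5 D or less. The p × q figures are therefore an upper limit for a given q.
- *That treatment has begun under every definition in the protocol.* It has not for a blade flap, where 12.1.1 and 12.1.2 look to laser contact. This makes the inconsistency wider, not narrower.

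The Manual of Procedures, to which 12.1.2 refers, is not available and parts of the SAP are blacked out. The absence of a handling rule is a statement about visible text only.

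**Conclusion.** The mismatch is real and stands in the current text. For subjects begun but completed in neither eye, withdrawal is left open; for a blade-flap complication before laser contact, 12.1.1 taken literally directs it. Either way, an eye in ITT can lack a Month 3 outcome for a reason tied to the procedure's failure.

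The size is unknown. At an assumed 2% lost in one arm, with all lost eyes failing, that arm's rate moves by 1.6 to 1.8 points against a planned 10-point effect. Loss confined to LASIK inflates the superiority claim, loss confined to SMILE counts against it, and equal loss is close to neutral. If aborts are rare the effect is negligible. This does not show that the trial is biased. It merits correction because data never collected at Month 3 cannot be recovered and the remedy is small.

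**What to change.** In the protocol, reconcile 9.2.1, 12.1.1, 12.1.2 and 12.4 with the definition of begun treatment in 11 and 15.2. For study follow-up, the investigator should not remove a subject once treatment has begun in either eye; subjects keep the right to withdraw. State that Month 3 manifest refraction is sought in every begun eye, including incomplete and converted eyes.

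In the SAP, state how begun-but-incomplete eyes count in the primary analysis, and add a sensitivity analysis that treats those with no Month 3 value as non-responders.

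The cost is consistent wording in four protocol sections, a few additional follow-up visits on the existing schedule and one extra analysis. The change concerns follow-up and analysis only; it proposes no rule for the surgical or clinical handling of an interrupted procedure.
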